Patients will be asked to rate their average level of pain in the past week on an 11-point scale (0-10) at baseline and at every time point as listed in table 1

Beck Anxiety Inventory (BAI): 21-item self-report inventory for measuring the severity of anxiety with high internal consistency. Each of the 21-items is rated on a 4-point Likert scale indicating how much each symptom bothered the patient in the previous month. This is a reliable and validated self-reported measure of anxiety. This will be performed at baseline, visit 7 and visit 10.

Postoperative Nausea and Vomiting Intensity scale (PONV): This is a 4-item questionnaire that is a valid, reliable, and responsive measure of clinically important postoperative nausea and vomiting. This will be performed at baseline, visit 2, 3, 4 and visit 9.

Revised American Pain Society Patient Outcome Questionnaire (APS-POQ-R): This questionnaire measures 6 aspects of patient quality including 1) pain severity and relief, 2) impact of pain on activity, sleep, and negative emotions, 3) side effects of treatment, 4) helpfulness of information about pain treatment, 5) ability to participate in pain treatment decisions, and 6) use of nonpharmacological strategies. This is a reliable, validated, and feasible questionnaire with high internal consistency. This will be performed at visit 3, 4 and 5.

Daily symptom surveys: Post-operative days 0-6, patients will complete a sheet with 16 questions about pain intensity, nausea, vomiting, and mobility. This will be performed at each visit starting at visit 4 through visit 9.

Patients will receive general anesthesia and post-operative analgesia per standard of care for liver transplantation.

Screen failures:

Subjects that are unable to complete visit 2 assessments, within the allotted window, will be a screen failure. Follow-up assessments will not be performed on screen failure subjects. However, subjects randomized to the device may continue to wear the device through the 120 hours regardless of screen fail status.

Auricular Neurostimulation Application:

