Postoperative ileus will be measured by need for nasogastric decompression for >48 hours; again, these events are routinely documented in the medical record as part of routine medical care. Time to sitting up in a chair and time to walking will be determined based on patient symptom surveys. Diet will be advanced as determined by the primary care team. Once the patients are able to tolerate oral intake, oral opioid medications will be started as needed. Escalation of this oral pain regimen will be noted but will not warrant exclusion from the study. Patients needing additional pain control with regional anesthesia techniques will be excluded from the study at that time. Patients will be discharged from the hospital once discharge criteria are met as determined by the treating physician. All patients will receive a standard narcotic pain medication prescription at discharge. The patients will receive an information sheet upon discharge with study and device information as well as contact information for study team members.

All patients will receive a phone call on device day 30 by the study coordinator, PI, or co-PI. At this time, the patients will again be asked to complete the numerical pain scale, BAI, symptom survey, and PONV score via telephone, and will be asked if he or she is still requiring narcotic pain medication, or if a refill of the narcotic pain medication was needed.

Device Removal

The study investigators, PI, or co-PI will remove the device after 120 hours of stimulation. The date and time of device removal will be recorded. If the patient is at home after 5 days, then the patient will be asked to remove it and to bring it to the next clinic appointment for proper disposal. If a device falls off completely, it should not be reapplied. If individual electrodes are dislodged, they can be reapplied with household adhesive tape. If a patient requests withdrawal from the study or removal of the device before the 5-day device life has expired, time of removal will be recorded.

Risk/Benefit Assessment

Overall risks/ discomforts involved are very minimal – Rare (event rate 1% - < 5%)

Possible risks/discomforts may involve:

Discomfort upon insertion of the electrodes for < 5 minutes - Rare (event rate 1% - < 5%)

Discomfort at the lead placement site > 5 minutes - Rare (1 % - < 5%)

Bleeding at the electrode site if the neurovascular bundle is penetrated - Rare (event rate 1% - < 5%)

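### Randomised subjects who miss visit 2 are called screen failures and lose follow-up, although the analysis is declared intention-to-treat

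*Combined protocol and SAP*

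**What the plan says.** Under Study Interventions, the Screen failures paragraph has three parts. First: "Subjects that are unable to complete visit 2 assessments, within the allotted window, will be a screen failure". Second: "Follow-up assessments will not be performed on screen failure subjects". Third: "subjects randomized to the device may continue to wear the device through the 120 hours regardless of screen fail status".

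The questionnaire schedule under Technical Details in the same section is:

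- Daily symptom surveys: "This will be performed at each visit starting at visit 4 through visit 9".
- Revised American Pain Society questionnaire (APS-POQ-R): "This will be performed at visit 3, 4 and 5".
- Nausea and vomiting scale (PONV): "This will be performed at baseline, visit 2, 3, 4 and visit 9".
- Beck Anxiety Inventory (BAI): "This will be performed at baseline, visit 7 and visit 10".

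The Intraoperative and Postoperative Protocol takes time to sitting and time to walking from the symptom surveys. It also states "All patients will receive a phone call on device day 30 by the study coordinator, PI, or co-PI". That call repeats several questionnaires and asks about continuing narcotic use and refills.

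Data Analysis & Statistical Considerations names opioid use after surgery as the primary endpoint. It declares ITT, imputes missing outcomes by multiple imputation under missing at random (MAR), and adds a complete case analysis. It does not define the ITT set or mention screen failures.

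**The concern.** A screen failure is ordinarily someone who never entered the randomised comparison. Here the label depends on an assessment listed separately from baseline, and it can fall on a subject already assigned to the device. Two analysts following this plan could analyse different populations.

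Dropping these subjects selects the analysed set on an event after randomisation and shrinks a small trial. Keeping them leaves their later questionnaires to be imputed, because the protocol tells staff not to collect them. Those data cannot be recovered afterwards.

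There is a second conflict. The day-30 call is promised to everyone, yet screen failures are to have no follow-up assessments. That call is the only place where the documents describe asking about narcotic use after discharge.

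**Working it through.** **1. Can the label fall after randomisation?** Yes. The third part of the paragraph speaks of subjects randomised to the device who have screen-failed. This agrees with Design & Procedures, where the device is placed before surgery, and with the schedule, which lists visit 2 separately from baseline.

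**2. What does the rule remove?** Reading the schedule from visit 3 onward:

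| Instrument | Scheduled | Lost |
|---|---|---|
| Symptom survey | visits 4–9 | all 6 |
| APS-POQ-R | visits 3, 4, 5 | all 3 |
| BAI | baseline, visits 7, 10 | both post-baseline |
| PONV | baseline, visits 2, 3, 4, 9 | visits 3, 4, 9 |

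Apart from any partial visit 2 data, imputation for these subjects has no post-baseline questionnaire values to draw on. The 0–10 pain scale follows Table 1, which is not visible, so its losses cannot be counted.

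**3. The plan's own power figures.** Two-sample t-test, noncentral t, two-sided 0.05, 80% power: 25 per group gives 0.809 (plan: 0.81) and 32 per group gives 0.711 (plan: 0.71). Both reproduce.

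**4. Power if subjects are dropped (assumed rates).** Selection of Subjects anticipates 35 per arm, for which the same method gives a detectable effect of 0.679 SD.

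| Random loss, both arms | n per arm | Power at 0.679 | Power at 0.71 |
|---|---|---|---|
| 0% | 35 | 80% | 83.3% |
| 5% | 33.25 | 77.9% | 81.4% |
| 10% | 31.5 | 75.6% | 79.2% |
| 20% | 28 | 70.4% | 74.2% |

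**5. Power if loss tracks the outcome.** Assume non-completion occurs when a latent normal variable, correlated ρ with the outcome, exceeds a threshold c common to both arms. At 20% control loss c = 0.842. The device effect moves the effective threshold to 0.842 + 0.679ρ, so device loss is 14.8% (ρ = 0.3) or 11.9% (ρ = 0.5). Among completers the arm mean shifts by ρφ(c)/(1−p), so the observed difference is:

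- ρ = 0.3: 0.679 − 0.3 × (0.350 − 0.271) = 0.656
- ρ = 0.5: 0.679 − 0.5 × (0.350 − 0.225) = 0.617

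Simulation (200,000 trials, 35 per arm) gives power of 70.2% and 68.1%. Random loss of the same size gives 71.6% and 72.1%. Selection therefore adds 1.4 and 4.0 points. At 10% control loss the figures are 75.5% and 73.9% (device loss 6.9% and 5.2%), against 76.1% and 76.6% for random loss.

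**6. Bias with no true effect.** The same formula, differenced between arms:

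- 20% vs 10%: ρ × (0.350 − 0.195) = 0.046 (ρ = 0.3) or 0.077 (ρ = 0.5) SD
- 10% vs 5%: ρ × (0.195 − 0.109) = 0.026 or 0.043 SD

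Simulated type I error is 5.3–5.4% and 6.0–6.1% in the first case, and 5.1% and 5.4% in the second. With equal 20% loss it is 4.9–5.0%.

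**7. Time to walking if subjects are kept and imputed.** Assume 20% control and 10% device non-completers, whose hazard is half that of completers, and no other difference. At time zero the ratio of average hazards is (0.9 + 0.1 × 0.5)/(0.8 + 0.2 × 0.5) = 0.95/0.90 = 1.06. A Cox fit over 6 days (400,000 per arm, exponential, daily hazard 0.25–0.40) gives 1.07–1.08. Imputing non-completers to resemble completers in their arm would show 1.00. With multipliers of 0.75 and 0.25 the Cox ratio is 1.03 and 1.12–1.14.

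**The case against.** The best defence is that ITT ordinarily means all randomised subjects, imputation covers any missing outcome, and nothing says screen failures leave the analysis. On that reading one clarifying sentence is missing. This answers the dropping scenario only if the label is ignored, and it does not answer the other branch: the protocol still forbids collecting the data that are then imputed.

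Several narrower points stand:

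- Harm to the primary endpoint is not shown. The documents do not state the source of opioid use or whether it would still be collected. Only ileus is expressly described as documented in the record. The wording there hints at wider record use, and escalation of oral pain medication is to be noted, but neither settles it.
- The losses that can be demonstrated are in questionnaires. BAI and APS-POQ-R are not named as endpoints, the other affected outcomes are called exploratory, and the study calls itself a pilot.
- Record data could enter the imputation model, which the plan does not restrict to questionnaires.
- Symptom surveys are placed on postoperative days 0–6 from visit 4, so visit 2 may be very early. Loss that tracks later recovery and differs by arm is then less plausible. Seven days do not map cleanly onto six visits, and Table 1 is not visible, so timing cannot be settled.
- The effect of 0.68 SD is back-solved for 35 per arm and is not the plan's figure. The plan already allows 20% dropout, which may overlap with this loss.

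These points limit the size of the concern. They do not remove the conflict in the text.

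**Conclusion.** The plan is wrong as written and should be corrected. Confidence in the textual conflict is high: randomised subjects can be labelled screen failures and denied follow-up under a declared ITT analysis, and no section says how they are analysed.

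The numerical effect is modest and rests on assumed rates, correlations and hazards. For losses of 5% to 20%, dropping subjects at random costs about 2 to 10 points of power, and outcome-related loss adds about 1 to 4 points. Null bias is 0.03 to 0.08 SD with unequal loss and nil with equal, similar loss. Its actual size and direction are unknown. The reason to act is that the missing data are avoidable and the analysed population is left open.

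**What to change.** Limit the screen-failure label to consented subjects not yet randomised, and add wording such as:

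> The ITT set is every randomised subject, in the arm assigned. A missed visit 2 assessment is recorded as missing. Unless consent is withdrawn or not reaffirmed, later assessments, including the day-30 call, are attempted. Opioid use and other outcomes are collected, from the medical record where available.

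Also:

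- State the data source for opioid use.
- Reconcile the Screen failures paragraph with the day-30 call.
- State that randomised subjects excluded for regional anaesthesia stay in the ITT set, for analysis only and with no change to their care.
- Report visit 2 non-completion by arm, with reasons.
- Optionally, add a missing-not-at-random sensitivity analysis. Use shifted imputed values for continuous questionnaire scores. For time to sitting and walking, use imputed event times with non-completers' hazard multiplied by 0.5 to 1, by arm.

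The cost is a short amendment and continued data collection for visit 2 non-completers. Their number is unknown; 5% to 20% of 70 would be about 4 to 14 subjects. Some questionnaires will still be missing, and the shift and hazard values in the optional analysis are a matter of judgement.

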Device placement will take approximately 5 minutes. The patient will remain at rest for the next 5 minutes. Care will be taken not to interfere with standard pre-operative procedures. If the electrodes become dislodged a qualified practitioner will re-apply them.

Subject will then undergo surgery as per standard of care. The patient's anesthesiologist will be informed ahead of time of the device placement. Anesthesiologist and operative room staff will be instructed to avoid manipulating the device while moving the patient or during the procedure.

Patients will be advised not to manipulate the device or immerse the device in water as it is water resistant but not water proof. If showering or washing hair, they should place a dry wash cloth or plastic covering over the area to protect the device. If the electrodes become dislodged a qualified practitioner will re-apply them.

Intraoperative and Postoperative Protocol

In those randomized to have the BRIDGE device, neurostimulation will be delivered below sensation threshold continuously for 120 hours, the duration of the device battery. The anesthesiology team will be informed of participation in the study prior to BRIDGE application. It will be discussed that any use of regional anesthesia or NSAIDs are not permitted in this study. If the anesthesiologist believes the patient has contraindications to other methods of analgesia or anesthesia, or if it may be in the patient's best

interest to incorporate regional anesthetic techniques, the patient will be excluded from the study. Operating room staff will be instructed to avoid manipulating the device while moving the patient or during the procedure. The device does not interfere with any monitoring routinely used in the operating room.

All patients will undergo general anesthesia per standard of care. There will be no intraoperative or postoperative use of regional pain therapies (i.e. epidural anesthesia, tranversus abdominis plan blocks); anesthetic plan will otherwise be per treating physician. Once the procedure is over and the patient is extubated and transferred to the postoperative care unit, both groups (those with the device and those without) will continue to receive postoperative pain control per standard of care, as determined by the anesthesia and surgical teams. During the hospitalization, the postoperative pain control in all patients (both groups) will be per standard of care (opioids) per the adult liver transplant protocol.

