Localized discomfort if the electrodes should become dislodged during the wearing of the device - Rare (event rate 1% - < 5%)

Localized dermatitis - Rare (event rate 1% - < 5%)

Drop in blood pressure - Rare (event rate 1% - < 5%)

Syncope (fainting) - Rare (event rate 1% - < 5%)

Adverse effects to supporting personnel

Skin piercing with percutaneous needles - Rare (event rate 1 % - < 5%)

There are numerous, possible direct and long-term benefits to the subjects in this study. The results of this study may provide important insights to the medical field regarding a new, non-pharmacologic therapy that could improve pain control and quality of life for patients undergoing liver transplantation. If effective, a significant decrease or prevention in post-operative opioid use would be a major breakthrough in healthcare. This treatment would then have the potential to be extrapolated to other post-operative settings and populations.

Data Analysis & Statistical Considerations

This randomized study and the subjects will be randomized 1:1 ratio to the treatment groups. The primary efficacy endpoint is opioid usage after surgery in the two groups, and the related secondary endpoint is pain score in the two groups at the end of surgery. Normality possible transformations to attain normality of these variables will be assessed. These variables will be analyzed using either a two-sample t-test or non-parametric Wilcoxon test, depending on whether the outcomes are normal or non-normal. Analysis will be conducted under Intent-To-Treat (ITT), and any missing outcome will be imputed under missing at random (MAR) using multiple imputation methods. In addition, complete case analysis will be conducted. Continuous outcomes, adjusted for covarites, will be examined using regression analysis. Significance of the results will be examined at a two-tailed 0.05 alpha level.

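### Randomised device subjects relabelled as screen failures may keep wearing the active device for 120 hours with follow-up assessments stopped, no safety recording specified and no defined place in the safety comparison

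*Combined protocol and SAP*

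**What the plan says.** The rule is in the Screen failures paragraph of Study Interventions. It has three parts:

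- The trigger: "Subjects that are unable to complete visit 2 assessments, within the allotted window, will be a screen failure".
- The consequence: "Follow-up assessments will not be performed on screen failure subjects".
- The exception for wear: "subjects randomized to the device may continue to wear the device through the 120 hours regardless of screen fail status".

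The device is active throughout. Under Intraoperative and Postoperative Protocol, "neurostimulation will be delivered below sensation threshold continuously for 120 hours, the duration of the device battery".

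Risk/Benefit Assessment lists discomfort at insertion and at the lead site, bleeding, discomfort from dislodged electrodes, dermatitis, a drop in blood pressure and syncope. Each is given a rate of 1% to under 5%.

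Three other places bear on the point:

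- **Intraoperative and Postoperative Protocol** ends with a day 30 telephone call, written for every patient without exception.
- **Device Removal** has the study team take the device off after 120 hours and record the date and time. A patient already at home removes it personally.
- **Data Analysis & Statistical Considerations** defines the trial's adverse events as infections and complications, compares their rates between groups, and names no safety population. Its intention-to-treat statement does not mention screen failures.

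**The concern.** Screen failure normally describes someone who never entered the trial. Here the label is applied to people who have been randomised and, in the device arm, already have percutaneous electrodes in place. Followed as written, the rule ends scheduled study assessment of exposed subjects while allowing their exposure to go on, and puts no safety recording in its place.

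Two things are at stake. First, device events during the remaining wear may not reach the study data. Dependence on wear time is clearest for dislodgement, dermatitis and lead-site discomfort; bleeding is tied to penetration of the neurovascular bundle and so belongs mainly to placement. Second, the analyst has no rule for whether these subjects are in the denominator of the between-group comparison or of any device-event rate. A label that usually means not in the study invites inconsistent handling.

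**Working it through.** **Step 1. Are these subjects exposed?** Yes. The device is placed after the baseline assessments and before surgery, and the wear exception speaks of subjects randomised to the device who continue to wear it.

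**Step 2. What study contact remains, and does it record device events?**

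| Contact | Applies to screen failures? | Device-event recording specified? |
|---|---|---|
| Pain, anxiety, nausea and quality questionnaires; symptom sheets | No, stopped | Little: symptom sheets cover pain, nausea, vomiting and mobility; only the APS-POQ-R has a general side-effects domain |
| Inpatient care | Yes | None routed to study data |
| Device removal | Not excluded | Date and time only |
| Day 30 call | Contradictory: written for every patient, but follow-up is stopped for screen failures | None listed: pain scale, BAI, symptom survey, PONV and narcotic use |

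**Step 3. Are they in the safety comparison?** No sentence removes them and no sentence includes them. The intention-to-treat statement could be read to retain them. Their place is undefined.

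**Step 4. How much information could be lost?** The plan gives no figure for this, so there is none to reproduce. The effect sizes under Power concern opioid use and do not bear on it.

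Inputs:

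- Device arm: 35, from Selection of Subjects.
- Event rate: 1% to under 5%, from Risk/Benefit Assessment. The 5% figure is the open upper limit.
- Share of the device arm lost to screen failure: not in the documents. I assume 10% to 30%. This leaves 31.5, 28 and 24.5 subjects, taken as 32, 28 and 24.

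Formulas, for n observed subjects and rate p:

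- Chance of at least one event: 1 − (1 − p)^n.
- One-sided 95% upper bound on the rate after zero events: 1 − 0.05^(1/n).

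| Observed n | Assumed loss | p = 1% | p = 5% | Bound after zero events |
|---|---|---|---|---|
| 35 | none | 1 − 0.99^35 = 29.7% | 1 − 0.95^35 = 83.4% | 1 − 0.05^(1/35) = 8.2% |
| 32 | 10% | 1 − 0.99^32 = 27.5% | 1 − 0.95^32 = 80.6% | 1 − 0.05^(1/32) = 8.9% |
| 28 | 20% | 1 − 0.99^28 = 24.5% | 1 − 0.95^28 = 76.2% | 1 − 0.05^(1/28) = 10.1% |
| 24 | 30% | 1 − 0.99^24 = 21.4% | 1 − 0.95^24 = 70.8% | 1 − 0.05^(1/24) = 11.7% |

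The drop in detection runs from 29.7 − 27.5 = 2.2 points to 29.7 − 21.4 = 8.3 points at a 1% rate, and from 83.4 − 80.6 = 2.8 points to 83.4 − 70.8 = 12.6 points at 5%. The table assumes that every observed subject is actively checked for the event, which the documents do not say, so it is illustrative only.

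**The case against.** The strongest reply is that the paragraph stops questionnaires, and questionnaires were never going to find dermatitis or a dislodged electrode. If device-event recording is missing, it is missing for every device patient, and the screen-failure rule does not create that gap. These are inpatients recovering from a liver transplant. Subjects are told before placement to report persisting discomfort, a qualified practitioner re-applies dislodged electrodes, removal is timed, and discharged patients receive a sheet with study-team contact details. None of this is limited to subjects who completed visit 2.

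Much of that stands. A reader might infer that these subjects go wholly unobserved; the contacts just listed do not support that. A reader might also infer that they are dropped from the safety count; no sentence says so, and intention-to-treat could keep them. Nor do the documents show that those who miss visit 2 are the sickest, so a favourable bias in the device's safety profile is a possibility and not a finding. The visit 2 window depends on Table 1, which I could not check, and a missed window may be logistical.

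What the reply does not remove is the rule itself. The remaining contacts carry no instruction to record device events, the denominator is unstated, and the stop contradicts the day 30 call. That the wider plan also lacks device-event recording widens the need for a fix.

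**Conclusion.** The point holds as a gap in specification and an internal conflict. Randomised, exposed subjects can be relabelled as screen failures and continue active wear to 120 hours with no study safety recording specified. Their place in the safety comparison is undefined, and two sections disagree on whether they are called at day 30.

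The effect is modest and its true size is unknown. Under assumed losses of 10% to 30% from 35 device patients, the chance of seeing at least one event falls by roughly 2 to 13 percentage points, depending on the loss and the event rate. This rests on the assumed loss, on the documents' 1% to 5% range, on equal risk in lost and retained subjects, and on active recording in those retained. If the lost subjects carried higher risk, more would be missed, but the documents give no basis for a figure.

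**What to change.** 1. **Screen failures paragraph.** State that questionnaires may stop for screen-failed subjects, but that adverse event and complication recording continues for all randomised subjects in both arms through day 30. For anyone in whom the device was placed, record ear-site events during wear and at removal. Covering both arms keeps the between-group comparison even.
2. **Data Analysis & Statistical Considerations.** State that the safety comparison includes all randomised subjects, and that device events are reported over all subjects in whom the device was placed, whatever their later status.
3. **Day 30 call.** Reconcile the stop on follow-up with the call written for every patient.

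Whether the device stays on after a screen failure is for the sponsor to decide; this point does not address it.

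The cost is a few sentences of amendment, plus brief notes and one call for a small number of subjects, by existing staff.
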